5.5.1.2. Mirvetuximab Soravtansine Dose Reduction Dose Levels

MIRV dose reduction will be as described in [Table 4](#).

Table 4: Mirvetuximab Soravtansine Dose Reduction Dose Levels

If the patient was receiving MIRV at:	Dose should be reduced to:
6.0 mg/kg AIBW	5.0 mg/kg AIBW
5.0 mg/kg AIBW	4.0 mg/kg AIBW
4.0 mg/kg AIBW	Permanently discontinue
Reduction of MIRV below 4.0 mg/kg will not be permitted. Dose re-escalation is not permitted.	

Abbreviations: AIBW = adjusted ideal body weight; MIRV = mirvetuximab soravtansine.

5.5.1.3. Monitoring and Management of Nausea and Vomiting

Treatment-related nausea (46% all grade; 1% Grade 3+) and vomiting (16% all grade; 1% Grade 3+) have been reported in patients treated with MIRV, despite premedication with dexamethasone. Therefore, it is recommended that an antiemetic (eg, 5-HT₃ serotonin receptor antagonists such as palonosetron, granisetron or ondansetron) medication is provided before each MIRV dose ([Section 5.8.1](#)). Additional antiemetics may be used any time at the discretion of the treating physician, according to institutional or other practice guidelines American Society of

Clinical Oncology (ASCO), ESMO, and NCCN. Patients should be advised to contact their treating physician at the first sign of vomiting or worsening nausea.

5.5.1.4. Monitoring and Management of Diarrhea

Mild to moderate diarrhea has been reported in patients treated with MIRV. Patients should be advised to contact their treating physician at the first sign of diarrhea. Patients may then be treated according to standard institutional practice. One suggested regimen would be the administration of loperamide 2 mg at the first sign of loose stool, with repeat dosing every two hours until symptoms resolve ([Wadler 1998](#)).

5.5.2. Ocular Disorders

Changes in visual acuity resulting from reversible keratopathy have been reported in other studies of DM4-containing immunoconjugates that use the SPDB linker ([Younes 2012](#)). Patients receiving MIRV in the Phase 1 and 3 trials (IMGN853-0401, IMGN853-0403) reported ocular AEs consistent with reversible keratopathy/corneal epitheliopathy.

5.5.2.1. Monitoring and Preventive Measures

In early dose escalation of Study 0401, a relationship was observed between MIRV plasma exposure and likelihood of an ocular event and response. Exposure-response modeling suggested that a dose of 6.0 mg/kg AIBW provided adequate exposure for response while also maintaining overall exposure within a range that decreased the potential for ocular AEs. Due to the observation of ocular disorders consistent with reversible keratopathy/corneal epitheliopathy in patients treated with MIRV, ocular function will be carefully monitored. Ocular symptom assessments will be performed at baseline and at Day 1 of every cycle thereafter ([Table 2](#)). Complete ophthalmologic exams will be performed in all patients at baseline and every other cycle thereafter if there is a TEAE reported.

Patients are advised to avoid using contact lenses while on MIRV. Baby shampoo and a soft cloth should be used to clean the eyes, and a warm compress at bedtime may be used to decrease any possible inflammation on the eyelid's surface. Please refer to [Section 5.4.2.1](#) and [Section 5.4.2.2](#) for details on the prophylactic use of steroid eye drops and lubricating artificial tears. The use of UVA/UVB sunglasses is recommended in full daylight during the study. The use of temporary lower punctal plugs to increase lubrication of the eyes is optional if lubricating artificial tears and corticosteroid eye drops are not sufficient. If patients report signs or symptoms of ocular disorders, including, but not limited to, blurred vision or eye irritation, the management and dose modification guidelines outlined in [Table 5](#) should be followed.

5.5.2.2. Management and Dose Modification Guidelines

If a patient develops ocular symptoms of any grade, the patient is required to have a complete examination by an ophthalmologist. If a patient develops \geq CTCAE Grade 2 ocular symptoms, treatment with MIRV must be interrupted. Treatment should not be interrupted solely for Grade 2 ocular signs (eg, Grade 2 keratopathy) unless they are also associated with Grade 2 ocular symptoms. Treatment with MIRV may resume if ocular symptoms improve to Grade 1 or baseline within 28 days of the next scheduled MIRV dose (refer to [Table 5](#) for details). If ocular

symptoms last longer than 28 days, resumption of MIRV, with or without dose reduction, may be considered for those patients who have experienced clinical benefit if agreed upon between the Sponsor and the Investigator. Subsequent eye examinations will be scheduled to occur in every other cycle going forward, from the time that the AE was initially reported, and at either the EOT visit or 30-Day Follow-up Visit after treatment discontinuation, even if the results of the patient’s ocular exam shows no obvious clinical findings. Management of treatment-emergent ocular AEs with inflammatory characteristics should include corticosteroid eye drops and/or other measures as indicated by an ophthalmologist.

Table 5: Management of Ocular Symptoms

Severity Grade (CTCAE v5.0)	Management	Guidelines for MIRV Dose Modifications
Grade 1	Complete eye exam as outlined in Schedule of Assessments (Table 2) Monitor for worsening symptoms	Continue MIRV dosing
Grade 2	Complete eye exam as outlined in Schedule of Assessments (Table 2) Repeat complete exam as clinically indicated Patients should have weekly symptomatic ocular assessments by the Investigator until the symptoms resolve to Grade 1 or baseline or are deemed to be irreversible by the Investigator	Hold MIRV dosing until AE has resolved to Grade 1 or better Patients with ocular symptoms lasting < 14 days may be allowed to resume MIRV at the same dose level Patients with ocular symptoms lasting ≥ 14 days but no more than 28 days may resume MIRV at one lower dose level Recurrence of Grade 2 toxicity on subsequent cycles despite best supportive care will require a MIRV dose reduction of one dose level
Grade 3	Complete eye exam as outlined in Schedule of Assessments (Table 2). Repeat complete exam as clinically indicated Patients should have weekly symptomatic ocular assessments by the Investigator until the symptoms resolve to Grade 1 or baseline or are deemed to be irreversible by the Investigator	Hold MIRV dosing Patients may be allowed to resume MIRV at a lower dose after AE has resolved to Grade 1 or better within 28 days Recurrence of Grade 3 toxicity on subsequent cycles despite best supportive care will require a MIRV dose reduction of one dose level
Grade 4	Complete eye exam as outlined in Schedule of Assessments (Table 2). Repeat complete exam as clinically indicated Patients should have weekly symptomatic ocular assessments by the Investigator until	Permanently discontinue MIRV

Severity Grade (CTCAE v5.0)	Management	Guidelines for MIRV Dose Modifications
	the symptoms resolve to Grade 1 or baseline or are deemed irreversible by the Investigator	

Abbreviations: AE = adverse event; CTCAE = common terminology criteria for adverse events; MIRV = mirvetuximab soravtansine.

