4.1.2. Dose and Schedule for Mirvetuximab Soravtansine

MIRV will be administered at 6 mg/kg on Day 1 of every 3-week cycle (Q3W).

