5.5.1. Treatment Criteria

In the absence of a TEAE that requires dose modification (as specified in the management guidance for a particular toxicity, see Section 5.5.1.1), a patient must meet the following criteria to receive MIRV at any cycle:

- ANC must be $\geq 1.5 \times 10^9/L$ (1,500/ μ L)
- Platelet count must be $\geq 100 \times 10^9/L$ (100,000/ μ L)
- All non-hematologic toxicities for which a causal association to study drug cannot be ruled out, must be \leq Grade 2 or returned to baseline; the exceptions to this rule being:
 - Treatment-emergent ocular disorders, which must have recovered to \leq Grade 1 or baseline
 - Treatment emergent pneumonitis which must have recovered to \leq Grade 1

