5.5.1.1. Mirvetuximab Soravtansine-Related Adverse Events

Dose modifications for MIRV-related AEs are described in [Table 3](#).

Table 3: Dose Modifications for Mirvetuximab Soravtansine-Related Adverse Events

Severity Grade (CTCAE v5.0)	Dose Modifications for MIRV ^a
Hematological	
Neutropenia	
Grade 2 and Grade 3	Hold drug until ANC is $\geq 1.5 \times 10^9/L$ (1500 / μ L) and resume at the same dose level
Grade 4	Hold drug until ANC is $\geq 1.5 \times 10^9/L$ (1500 / μ L) and then resume at one lower dose level
Febrile neutropenia Grade 3 or 4 (with a single temperature reading $\geq 38.3^\circ C$ or a sustained temperature of $> 38^\circ C$ for > 1 hour)	Hold drug until ANC is $\geq 1.5 \times 10^9/L$ (1500 / μ L) and then resume at one lower dose level
Thrombocytopenia	
Grade 2 and Grade 3	Hold drug until PLT count is $\geq 100 \times 10^9/L$ (100,000/ μ L) and resume at same dose level
Grade 3 associated with clinically significant bleeding that requires transfusion therapy and Grade 4	Hold drug until PLT count is $\geq 100 \times 10^9/L$ (100,000/ μ L) and then resume at one lower level
Non-hematological	
Nausea and Vomiting	
Grade 3 (despite use of optimal antiemetics)	Hold drug until resolved to \leq Grade 1, then resume at one lower level
Grade 4	Permanently discontinue
Diarrhea	
Grade 3 (despite use of optimal anti-diarrheal treatment)	Hold drug until resolved to \leq Grade 1, then resume at one lower level
Grade 4	Permanently discontinue
Ocular Disorders	Refer to Section 5.5.2
Noninfectious Pneumonitis	Refer to Section 5.5.3
Infusion-related Reactions	Refer to Section 5.5.5

Table 3: Dose Modifications for Mirvetuximab Soravtansine-Related Adverse Events (Continued)

Severity Grade (CTCAE v5.0)	Dose Modifications for MIRV ^a
All Other Non-hematological Toxicities (except AEs related to underlying disease, Grade 3 fatigue, isolated symptomatic Grade 3 biochemistry laboratory abnormalities that last for < 7 days including electrolyte abnormalities that respond to medical intervention)	
Grade 3	Hold drug until resolved to ≤ Grade 1, then resume at one lower level For any Grade 3 hepatic toxicity that does not resolve to baseline within seven days, an abdominal CT scan must be performed to assess whether it is related to disease progression.
≥ Grade 3 Cardiac events (excluding Grade 3 hypertension)	Permanently discontinue
Grade 4 non-hematological toxicities	Permanently discontinue

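### Protocol 5.5.2.2 and Table 5 count the 28-day ocular limit from different starting points, so whether Sponsor agreement is needed depends on which sentence a site follows

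*Protocol*

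**What the plan says.** Protocol Section 5.5.2.2 requires MIRV to be interrupted for ocular symptoms of CTCAE Grade 2 or higher. It then states the limit for resuming in four places:

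- **Text, first sentence:** "Treatment with MIRV may resume if ocular symptoms improve to Grade 1 or baseline within 28 days of the next scheduled MIRV dose", with a pointer to Table 5 for details.
- **Text, next sentence:** the rule changes when "symptoms last longer than 28 days, resumption of MIRV, with or without dose reduction, may be considered". This later route is restricted; it is open only "for those patients who have experienced clinical benefit if agreed upon between the Sponsor and the Investigator".
- **Table 5, Grade 2:** symptoms of under 14 days allow the same dose level. Symptoms lasting at least "14 days but no more than 28 days may resume MIRV at one lower dose level". There is no entry beyond 28 days.
- **Table 5, Grade 3:** "Patients may be allowed to resume MIRV at a lower dose after AE has resolved to Grade 1 or better within 28 days". No start date is given, and again there is no entry beyond 28 days.

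Two other rules bear on the point. Section 5.5.1 lists a recovery condition for redosing: "Treatment-emergent ocular disorders, which must have recovered to" Grade 1 or less, or baseline. Section 5.5.6 and the footnote to Table 3 set a general limit of 21 days after the missed dose, which gives way where the guidance for a particular toxicity says otherwise.

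**The concern.** The two sentences of text stand next to each other and use the same number, 28, but measure different things. The first measures from a date on the dosing calendar. The second measures how long the symptoms have been present. They agree only when symptoms begin on the day the next dose is due.

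The second sentence carries the safeguard: beyond its limit, redosing needs clinical benefit and agreement between Sponsor and Investigator. A site that follows the first sentence can redose a patient with well over 28 days of symptoms without that step, and Table 5 does not say at what dose. The study has no independent data monitoring committee (Section 12.5.2) and plans about 98 centers, so uniform handling depends on the written rule. Ocular events are a known effect of this drug. Section 1.6.2 reports blurred vision in 40% of MIRV patients in the earlier Phase 3 study, where the safety profile was predominantly low grade.

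**Working it through.** No figure in the plan needs reproducing. The check is day arithmetic.

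**Inputs.** Cycle length 21 days (Section 4.1.2), so a dose on Day 1 puts the next due dose on Day 22. Ocular limit 28 days (Section 5.5.2.2). General limit 21 days after the missed dose (Section 5.5.6). Let *d* be the cycle day on which symptoms begin, and count duration as recovery day minus onset day.

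**Formulas.**
- Next-dose clock: the limit falls on Day 22 + 28 = 50, so the symptom duration it tolerates is 50 − *d*.
- Duration clock: 28 days, so the limit falls on Day *d* + 28.
- Gap: (50 − *d*) − 28 = 22 − *d*.

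| Onset day *d* | Days tolerated, next-dose clock | Days tolerated, duration clock | Gap (days) | Duration limit falls on |
|---|---|---|---|---|
| 1 | 49 | 28 | 21 | Day 29 |
| 8 | 42 | 28 | 14 | Day 36 |
| 15 | 35 | 28 | 7 | Day 43 |
| 21 | 29 | 28 | 1 | Day 49 |
| 22 (due date) | 28 | 28 | 0 | Day 50 |

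For onset on Days 1 to 21, the rules conflict for every duration from 29 days up to 50 − *d*. Across onset days this spans 29 to 49 days.

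**Example.** Symptoms begin on Day 8 and recover on Day 45, a duration of 45 − 8 = 37 days. The first sentence allows resumption, because Day 45 is before Day 50. The next sentence requires clinical benefit and agreement, because 37 exceeds 28. Table 5 supplies no dose: its Grade 2 bands end at 28 days, and its Grade 3 row covers only resolution within 28 days of an unstated start.

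**Comparison with the general limit.** This falls on Day 22 + 21 = 43. A limit counted from onset falls earlier when *d* + 28 < 43, that is, for *d* < 15.

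**Dose beyond 28 days.** Table 4 steps are 6.0, 5.0 and 4.0 mg/kg. Resuming without reduction instead of one level down means 6.0/5.0 = 1.20 (20% higher) or 5.0/4.0 = 1.25 (25% higher).

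**The case against.** **The clock.** The best defense is that the first sentence merely extends the general retreatment clock from 21 to 28 days after the missed dose, and that the second sentence is its complement, loosely worded. This is a plausible account of the intent, but it does not remove the conflict. Table 5 Grade 2 plainly counts symptom duration, so on this reading a patient with 29 to 49 days of symptoms may resume and still has no dose in Table 5. It is also fair to say that counting from onset is stricter than the general limit for early onsets. That is a real cost and is stated under the fix.

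**A stronger reading about dose.** A reader might infer that the protocol wrongly returns patients to full dose after the longest toxicity, and that the option must be removed. There is a real asymmetry: Table 5 requires a lower dose for Grade 2 symptoms of 14 to 28 days and for Grade 3 symptoms resolving within 28 days, while the over-28-day sentence does not. The documents do not support calling this an error, for these reasons:

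- The route is conditional on clinical benefit and Sponsor-Investigator agreement.
- Similar discretion appears elsewhere. Section 5.5.6 lets a benefiting patient continue by agreement, with no dose stated. Table 6 lets Grade 2 pneumonitis resume at the same or one lower level after discussion with the Sponsor.
- Table 3 requires one lower level for other Grade 3 non-hematological toxicities, exceptions apart, but sends ocular disorders to Section 5.5.2, so that row does not govern them.
- Table 5 requires a one-level reduction if Grade 2 or Grade 3 toxicity recurs in later cycles despite supportive care.
- Section 5.5.2.1 links exposure to response as well as to ocular events, so reducing the dose is a trade-off.
- Resuming without reduction means resuming at the current level, which is 6.0 mg/kg only if there was no earlier reduction.

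**Conclusion.** The clock conflict holds. It is a contradiction in a safety rule, and more than missing detail: the same patient is subject to the agreement step under one sentence and not under the other. The gap is 22 − *d* days: 21 for onset on Day 1, 1 for onset on Day 21, and none on the due date. In the gap, Table 5 gives no dose. This should be corrected.

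The looser dose rule beyond 28 days is a secondary observation for the Sponsor to consider, not a required change.

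The result assumes dosing on the 21-day schedule, and that duration is counted from symptom onset. The text implies the latter but does not write it as a date; the duration bands in Table 5 Grade 2 support it. The documents give no distribution of onset days and no rate of Grade 2 or 3 ocular symptoms beyond 28 days, so neither an average gap nor a patient count can be stated. Nobody should infer a problem with the primary analysis: the ORR test and its sample size do not depend on this rule.

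**What to change.** Use one clock throughout, namely symptom duration from onset of the Grade 2 or higher symptom:

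1. In the first resumption sentence of Section 5.5.2.2, replace the reference to the next scheduled dose with *within 28 days of onset of the Grade 2 or higher symptom*.
2. In Table 5 Grade 3, write *within 28 days of onset*.
3. Add to Table 5, Grades 2 and 3: *Symptoms lasting > 28 days: may resume only after recovery to Grade 1 or baseline, with clinical benefit and Sponsor-Investigator agreement, dose level per that agreement*. Naming recovery here is useful because the over-28-day sentence omits it, and the Section 5.5.1 list is introduced as applying when no adverse event requires dose modification.

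Optionally, the Sponsor should consider making one lower level the default beyond 28 days, or state why the current level may be kept. Under such a default, a patient already at 4.0 mg/kg would stop under Table 4 unless the agreement provided otherwise.

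**Cost.** Items 1 to 3 change wording only, with no new data or analysis. Agreement is triggered earlier than under the next-dose clock: for Day 1 onset on Day 29, 7 days after the due dose, instead of Day 50. For onset before Day 15 it also comes earlier than the general limit of Day 43. Missing the limit triggers the agreement step, not a stop.

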5.5.3. Monitoring of Noninfectious Pneumonitis

Noninfectious pneumonitis has been observed after the administration of MIRV. Noninfectious pneumonitis may result in fatigue, shortness of breath, cough, or respiratory distress. Drug-induced pneumonitis may be immediately life threatening. If a patient presents with signs or symptoms consistent with pneumonitis and/or other clinically meaningful signs or symptoms of pulmonary toxicity, the patient should be immediately evaluated. Patients are advised to notify their treating physician immediately if they experience new or worsening shortness of breath, cough, or respiratory distress. Patients who are asymptomatic may continue dosing of MIRV with close monitoring.

The management and treatment guidelines outlined in [Table 6](#) should be followed.

Table 6: Management of Noninfectious Pneumonitis

CTCAE v5.0 Grade	CTCAE v5.0 Definition	Medical Management of Pneumonitis	Guidelines for Dose Modifications^a
Grade 1	Asymptomatic; clinical or diagnostic observations only; intervention not indicated	
 • Radiologic assessments (CT scan and/or chest x-ray) should be performed as clinically indicated. • Monitor for pulmonary symptoms. 	
 • Continue dosing in asymptomatic patients and monitor closely.
Grade 2	Symptomatic; medical intervention indicated; limiting instrumental ADL	
 • Radiologic assessments (CT scan and/or chest x-ray) should be performed as clinically indicated. • Patient must be evaluated by a pulmonary specialist. • Treatment with corticosteroids may be indicated as recommended by a pulmonary specialist and/or institutional guidelines. 	
 • Hold dosing until symptoms resolve to \leq Grade 1. • MIRV may be resumed at same dose level or one dose level lower after discussion with the Sponsor.
Grade 3	Severe symptoms; limiting self-care ADL; oxygen indicated	
 • Radiologic assessments (CT scan and/or chest x-ray) should be performed as clinically indicated. • Patient must be evaluated by a pulmonary specialist. • Treatment with corticosteroids until resolution of symptoms may be indicated as recommended by a pulmonary specialist and/or institutional guidelines. 	
 • Permanently discontinue MIRV.
Grade 4	Life-threatening respiratory compromise; urgent intervention indicated (eg, tracheotomy or intubation)	
 • Bronchoscopy with lavage and/or biopsy when clinically feasible should be performed. • The pneumonitis event must be followed until resolution. 	

Abbreviations: ADL = activities of daily living; AE = adverse event; CT = computed tomography; MIRV = mirvetuximab soravtansine.

^a Failure to meet retreatment criteria within 1 cycle (21 days) after the missed dose due to insufficient recovery from a treatment-related toxicity will result in treatment discontinuation unless otherwise specified in the management guidance for a particular toxicity.

5.5.4. Management of Electrolytes Imbalance

Prompt attention should be given to the correction of potential electrolytes imbalance, especially hypokalemia and hypomagnesemia.

5.5.5. Potential Infusion-related Reactions

Some patients treated with IV infusions of therapeutic drugs have experienced concurrent infusion-related reactions (IRR) (see CTCAE Version 5.0). The signs and symptoms may vary and include for example, headache, fever, facial flushing, pruritus, myalgia, nausea, chest tightness, dyspnea, vomiting, erythema, abdominal discomfort, diaphoresis, shivers, lightheadedness, hypotension, palpitations, and somnolence. Anaphylaxis might occur at any time during an infusion. Before any infusion is started, appropriate medical personnel, medication (eg, epinephrine, inhaled beta agonists, antihistamines, and corticosteroids), and other required resources to treat anaphylaxis must be readily available. In general, Investigators should manage acute allergic or hypersensitivity reactions according to Institutional practices. General guidelines for the management of acute IRRs and for subsequent retreatment are provided in [Table 7](#). Delayed IRRs may occur; therefore, patients should be advised to seek immediate medical treatment if symptoms newly develop and/or recur after discharge from clinic.

Patients who experience \geq Grade 2 IRR during or immediately after administration of MIRV will have blood drawn for determination of drug concentration and ADAs to MIRV. The sample should be obtained within three hours of the onset of the reaction and one week later. Such patients should undergo all scheduled efficacy and safety evaluations.

Table 7: Management Guidelines for Potential Infusion-Related Reactions

Infusion Reaction CTCAE v5.0 Severity Grade	Management
Grade 1: Mild, transient reaction	
 • Maintain infusion rate unless progression of symptoms to \geq Grade 2; if symptoms worsen, refer to guidelines below. • Promethazine (or equivalent) 150 mg PO per day (Q4h) PRN for nausea • Diphenhydramine (or equivalent) 25-50 mg PO or IV PRN • Methylprednisolone (or equivalent) 125 mg IV PRN
Grade 2: Moderate	
 • Interrupt infusion and disconnect infusion tubing from patient • Promethazine (or equivalent) 150 mg PO per day (Q4h) PRN for nausea • Diphenhydramine (or equivalent) 25-50 mg PO or IV PRN • Acetaminophen (or equivalent) 650 mg PO PRN • Methylprednisolone (or equivalent) 125 mg IV PRN • After recovery from symptoms, resume the infusion at 50% of the previous rate and if no further symptoms appear, gradually increase rate until infusion is completed. • For subsequent dosing in future cycles, patients should be pre-medicated with Dex (or equivalent) 8 mg PO BID the day before drug administration and acetaminophen (or equivalent) 650 mg PO and diphenhydramine (or equivalent) 25-50 mg PO 30-60 min before dosing.
Grade 3: Severe, prolonged reaction not rapidly responsive to symptomatic medication and/or brief interruption of infusion; recurrence of symptoms after initial improvement; hospitalization indicated for clinical sequelae OR Grade 4: Life-threatening consequences, urgent intervention indicated	
 • Immediately stop infusion and disconnect infusion tubing from patient. • Administer diphenhydramine (25-50 mg) IV (or equivalent) • Administer IV steroids (methylprednisolone (or equivalent) up to 0.5mg/kg Q 6h) to treat ongoing reaction and prevent recurrence • Administer bronchodilators (nebulized albuterol/salbutamol, 2.5-5 mg in 3 mL of saline or equivalent) as medically indicated • Administer normal saline as medically indicated • Administer epinephrine (0.2-0.5 mL of a 1:1000 dilution (0.2-0.5 mg) SQ or IM) as medically indicated. Epinephrine should only be used if all other treatment methods fail to manage the IRR. • Advise patient to seek emergency treatment and notify Investigator/clinic if the infusion-related symptoms recur after discharge from clinic. • Report as an SAE (see Section 8.1.1.2). • Permanently discontinue study medication treatment

Abbreviations: BID = twice a day; CTCAE = common terminology criteria for adverse events; Dex = dexamethasone; IM = intramuscular; IRR = infusion-related reaction; IV = intravenously; PO = orally; PRN = as needed; SAE = serious adverse event; SQ = subcutaneous.

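### Table 7 makes epinephrine a last resort for Grade 4 as well as Grade 3 infusion reactions, with no exception for the life-threatening grade

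*Protocol*

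**What the plan says.** The last row of Table 7 (Protocol Section 5.5.5) covers two grades, joined by OR, with one list of actions. Grade 3 is a severe or prolonged reaction that does not settle quickly with symptomatic drugs or a short pause, or that recurs or needs hospital admission. The other label is "Grade 4: Life-threatening consequences, urgent intervention indicated".

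The row's list includes:

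- stopping the infusion at once, IV diphenhydramine and IV steroids, all without condition;
- two conditional treatments, "Administer bronchodilators (nebulized albuterol/salbutamol, 2.5-5 mg in 3 mL of saline or equivalent) as medically indicated" and "Administer normal saline as medically indicated";
- an epinephrine bullet of two sentences. The first is "Administer epinephrine (0.2-0.5 mL of a 1:1000 dilution (0.2-0.5 mg) SQ or IM) as medically indicated". The second is "Epinephrine should only be used if all other treatment methods fail to manage the IRR";
- SAE reporting and "Permanently discontinue study medication treatment".

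The text before the table warns: "Anaphylaxis might occur at any time during an infusion". It requires staff, drugs and other resources for treating anaphylaxis to be at hand before any infusion, and epinephrine is among the four drug types it gives as examples. It then says that acute allergic or hypersensitivity reactions are in general to be handled by institutional practice, and it introduces Table 7 as general guidance for acute infusion reactions and later retreatment.

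**The concern.** A step-up order makes sense for a prolonged Grade 3 reaction, where there is time to see whether antihistamine, steroid and supportive measures work. The row applies the same order to Grade 4, which it defines by threat to life and need for urgent action. Nothing in the row separates the two grades.

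At stake is delayed treatment in a life-threatening reaction at a site that follows the table as written. This is a point of patient safety and drafting. It has no bearing on the response-rate endpoint, the sample size or any planned analysis.

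**Working it through.** There is no planned quantity to reproduce, so the check is a reading of the text.

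1. **The one figure in the bullet.** A 1:1000 dilution is 1 mg/mL, so 0.2 to 0.5 mL × 1 mg/mL = 0.2 to 0.5 mg, as stated. The dose is internally consistent. The problem lies only in when it may be given.

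2. **The two sentences of the bullet.** They pull in different directions but do not strictly contradict each other. The second can be read as defining when epinephrine counts as medically indicated, namely after everything else has failed. On that reading the restriction applies to every reaction in the row, Grade 4 included. Reconciling the sentences therefore confirms the problem.

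3. **The row label against the bullet.** Grade 4 calls for urgent intervention. The other listed actions are urgent interventions too, so the label does not by itself put epinephrine first. It does sit badly with holding back one of the listed emergency drugs until all the others have failed. The row has no Grade 4 exception.

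4. **Section text against the table.** Section 5.5.5 wants epinephrine ready for anaphylaxis but does not say when to give it. Neither the rest of the Protocol nor the SAP does so. SAP Section 6.2.2 deals with infusion-related reactions only as tabulated adverse events found by a hypersensitivity query. The Table 7 bullet is the only instruction on when and how to give the drug, and it is the one that restricts it.

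5. **Does the table reach anaphylaxis?** For: anaphylaxis is raised inside the infusion-reaction section, whose listed signs include dyspnea, chest tightness and hypotension, and there is no separate instruction for it. Against: the institutional-practice sentence comes between the anaphylaxis warning and the table, and the table never names anaphylaxis. The text does not decide the matter. The Grade 4 problem stands either way.

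6. **Size.** The expected number of affected patients would be the number treated times the probability of a Grade 3 or 4 reaction (or of Grade 4 alone). The documents give about 110 planned patients and no such probability, so the product cannot be formed.

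**The case against.** The best defence is that Table 7 is subordinate guidance. Section 5.5.5 makes institutional practice the general rule for allergic reactions before it mentions the table, and the restricting sentence is advisory in tone and speaks only of managing the infusion reaction. Section 12.7 provides for immediate departure from the protocol to remove a hazard, and adherence to the protocol includes adherence to the institutional-practice sentence. Section 5.4.1 also requires premedication before every infusion. These points make harm less likely, and many sites would probably act well regardless. But the deferral is general and mentions neither Grade 4 nor the order of treatments, whereas the restriction is specific and sits in the table staff would consult. Under Section 12.7 a departure must be fully documented, which would cast prompt epinephrine in a Grade 4 reaction as a deviation.

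A second objection is that the documents set no order among the emergency drugs. That is correct: they do not establish that epinephrine must come first, and this point does not rest on that claim.

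Three stronger readings are tempting but unsupported:

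- **That the bullet contradicts itself.** The sentences are in tension but can be read together.
- **That the protocol makes epinephrine a last resort in anaphylaxis.** Whether the table governs anaphylaxis is left open.
- **That exposure can be sized.** A reader might count two unconditional treatments and up to two conditional ones ahead of epinephrine, but the list is unnumbered, sets no waiting times and does not forbid giving treatments together, so the count does not measure delay. A reader might also reason that permanent discontinuation allows one such reaction per patient, hence about 110 at most. That is simply the planned sample size and says nothing about risk.

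**Conclusion.** The point holds as a patient-safety correction that should be made. As written, Table 7 leaves epinephrine until last in Grade 4 reactions, which the same row calls life-threatening, and it may do so in anaphylaxis. Confidence is high that the wording says this. How often it would matter is unknown: the number of patients affected cannot be estimated from the documents.

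The harm rests on two assumptions: that some site follows the sentence literally despite the general deferral to local practice, and that waiting for other treatments to fail is undesirable in a reaction needing urgent intervention. No statistical element of the trial changes.

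**What to change.** Change the epinephrine bullet in one of two ways.

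- **Option 1:** delete the last-resort sentence and extend the first sentence so that epinephrine is given when medically indicated and per institutional practice. This is the simpler edit and brings the table into line with the section text. The stated treatment order for prolonged Grade 3 reactions is lost.
- **Option 2:** replace the sentence with: *For Grade 3 reactions without anaphylaxis, reserve epinephrine for cases in which the other treatments have failed; for Grade 4 reactions or anaphylaxis, give epinephrine without waiting for other treatments to fail, per institutional practice.* This keeps the Grade 3 order and gives a positive instruction where the present text has none. Because the documents set no order for anaphylaxis, the sponsor's clinical staff should confirm that clause.

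The cost is a one-bullet amendment and a clarification to approximately 98 centers. Section 12.7 requires written ethics approval before a change takes effect, permits expedited review of minor changes, and waives prior approval where an immediate hazard must be removed. No new procedures, staff or patients are needed.
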